8.4 CYBERKNIFE TREATMENT DELIVERY

- 8.4.1 The prescribed PTV dose of 36.25Gy shall be given in 5 fractions using the CyberKnife.
- 8.4.2 Bowel/bladder preparation: patients will be advised to adhere to a low-gas, low-motility diet, starting at least one day prior to treatment. A fleets enema shall be administered 1-2 hours prior to treatment. If prostate movement remains significant despite these measures, a small-diameter rectal tube may be placed during treatment to vent gas. Patients shall urinate immediately prior to each treatment.
- 8.4.3 Treatment should be completed with 11 days; overall treatment time should be no less than 88 hours, with no less than 12 hours between any two fractions.
- 8.4.4 At least three fiducials should be identified for each treatment. If fewer than three fiducials can be tracked, then additional fiducials will be placed, and the patient replanned. Every effort will be made to treat using rotational corrections. The treatment system will be set to record rotations on the treatment printout. On a given treatment, if rotational corrections are not possible, treatment may continue, with rotational deltas recorded, as long as these remain below 2 degrees. For subsequent treatments, diet changes or additional bowel preparations will be made, and/or rectal tube placed, and treatment shall be attempted using rotational corrections. If treatment proceeds without rotational corrections, the therapist shall inform the attending radiation oncologist, and record the duration of treatment performed without rotations.
- 8.4.5 On the day of the CyberKnife treatment, the patient will be taken into the CyberKnife system treatment room, set up in their respective immobilization devices and positioned on the CyberKnife couch. X-rays will be taken with the

DDDDDDD57

CyberKnife system to ensure that the tumor is aligned in a manner consistent with the position in which the treatment plan CT image was taken. Imaging should occur every 1-3 nodes, per the discretion of the attending physician. Fiducial locations in the images will be extracted and compared to the fiducial locations in the CT scans to estimate target movements. The following planning and treatment information shall be recorded for every plan and fraction delivered: set-up time required, number of nodes treated, number of nodes treated with rotational corrections, number of nodes imaged, and total treatment time. This data will be collected onto Case Report Forms.

- 8.4.6 All planned nodes will be treated whenever possible. If treatment must be terminated prematurely on fractions 1-4, compensate as follows. If 2/3 or more of all non-zero nodes were treated, then the untreated nodes plus the full next fraction should be treated on the next treatment day (this should introduce an error of < 5% in BED delivered). If fever than 2/3 of the non-zero nodes were treated, then the untreated portion of this fraction (only) will be made up for on the following day. The subsequent fraction shall be delivered on the next treatment day. If treatment must be terminated prematurely on the fifth fraction, and 90% of the non-zero nodes were treated, then no further treatment shall be given (this should introduce an error of < 5% for total BED delivered). If fever than 90% of the non-zero nodes were treated, then the deficit shall be delivered on the following treatment day. All such variations shall be recorded.
- 8.4.7 WORK EFFORT: for all member of the treatment team (therapist, physicist, radiation oncologist, and urologist), time spent actively involved with treatment shall be recorded. Also, required on-site supervisory time will be recorded.

9.0 PATIENT ASSESSMENTS AND TOXICITY

	Pre- entry	Follow-up interval: months post therapy						Years post therapy		
Assessment		day 5	1 wk	1	3	6	12	18	24 (every 6 mo up to 5 years)	6-10
History	X			X	X	X	X	X	Xb	
Physical exam (DRE)	X				X	X	X	X	Xb	
ECOG Performance Scale	X				X	X	X	X	Xb	
Prostate Biopsy & Gleason score ^a	X								X	
PSA	X				X	X	X	X	Xb	X
Prostate volume assessment	X									
CBC, platelets	X									
BUN, creatinine	X									
Testosterone	X			X	X	X	X	X	X^{c}	X^{c}
Toxicity evaluation	X	X	X	X	X	X	X	X	X^{b}	X
AUA score	X	X	X	X	X	X	X	X	X*	X
SF-12	X			X		X	X		X*	
EPIC-26 Questionnaire	X			X		X	X		X*	X
SHIM Questionnaire	X			X		X	X		X*	X
Utilization of Sexual Rx/Devices	X			X		X	X		X*	
a. Central review of path	ology; bio	psy recon	mend	led a	at 2	yrs,	& re	equir	red at time of failure	_

	110 01 001
b. Continue every 6 months through to year 5	
c. Testosterone levels will be monitored until the 24 month follow-up visit and will be optionally measured at follow-up visits out to 10 years.	
* Continue every 12 months through year 5;	

- 9.1 EVALUATION DURING TREATMENT & FOLLOWING TREATMENT
 - 9.1.1 PRE-ENTRY ASSESSMENT: see section 4.7.
 - 9.1.2 Stereotactic radiosurgery is an outpatient procedure. Patient management immediately after the procedure will follow routine patient care guidelines as determined by the physician. Subjects will be provided instructions on who to call with specific contact information, in the event they experience any untoward effects following treatment. In the event a subject experiences any untoward effects following CyberKnife treatment, information specific to the patient's condition and symptoms, treatment intervention required, and hospital stay and course will be recorded for purposes of clinical evaluation.
 - 9.1.3 ACUTE ASSESSMENT: Patients will have toxicity evaluation and AUA score on the last day of treatment.
 - ASSESSMENTS FOLLOWING TREATMENT: at one week after treatment. 9.1.4 (allowed window: +/- 3 days), toxicity and AUA score will be evaluated. At 1 month (+/- 7 days) following treatment, patients will be assessed for acute toxicity, and will fill out AUA form, SF-12, EPIC-26, SHIM and Utilization of Sexual Rx/Devices. At 3, 6, 12, 18, and 24 month (+/- 2 wks) intervals (and every 6 months thereafter, through year 5, patients will be seen and evaluated, including a history, physical exam, ECOG performance status, PSA, toxicity evaluation, and AUA score. In addition, at 6 months, 12 months and annually thereafter, the SF-12, EPIC-26, SHIM and Utilization of Sexual Medications/Devices will be administered. After the 5 year follow-up patients will be seen yearly through year 10 (allowed window: +/- 1 month) and the following will be performed: PSA, toxicity evaluation, and the following questionnaires will be administered: EPIC -26; AUA; SHIM. Examination and studies may be done at outside facility. A serum total testosterone will be measured at month 1 and every PSA through year 2.
 - 9.1.5 PROSTATE BIOPSY will be performed at time of biochemical or local clinical failure, and is encouraged at 2 years following treatment and at time of distant failure.
 - 9.1.6 BONE SCAN will be performed at the time of biochemical failure, or when the patient develops signs of symptoms suggesting metastatic disease.
- 9.2 CRITERIA FOR TOXICITY
 - 9.2.1 ACUTE AND LATE TOXICITY
 - 9.2.2 Acute side effects (<=90 days of treatment start) will be assessed using the NCI Common Toxicity Criteria version 3.0 (see appendix V).
- 9.3 QUALITY OF LIFE ASSESSMENTS
 - 9.3.1 SF-12: The SHORT FORM-12 Health Survey measures generic health status relevant across different age, disease, and treatment groups. It provides a comprehensive, psychometrically sound assessment of health status from the

ACCP001.4

- patient's point of view by scoring responses to standard questions. The SF-12 is self-administered, and can usually be completed in less than 3 minutes without assistance.
- 9.3.2 EXPANDED PROSTATE CANCER INDEX COMPOSITE (EPIC)-26: is a validated comprehensive instrument developed to assess patient function and bother after prostate cancer treatment. It was developed by an expert panel of urological oncologists, radiation oncologists (including those with brachytherapy expertise), survey researchers, and prostate cancer nurses, to address symptoms related to radical prostatectomy, external beam radiotherapy, prostate brachytherapy, and hormonal symptoms. See appendix VI.
- 9.3.3 AMERICAN UROLOGICAL ASSOCIATION (AUA) SYMPTOM INDEX: Also known as the International Prostate Symptom Score (IPSS), this widely used index assesses urinary symptom bother. See appendix VI.
- 9.3.4 SEXUAL HEALTH INVENTORY FOR MEN (SHIM): is a widely used, internationally validated and sensitive instrument for assessing erectile dysfunction⁷⁰.
- 9.3.5 UTILIZATION OF SEXUAL MEDICATIONS/DEVISES: provides context for interpreting the sexual domain score of the EPIC questionnaire.
- 9.4 CRITERIA FOR DISEASE CONTROL: intervals will be measured from enrollment date.
 - 9.4.1 BIOCHEMICIAL DISEASE-FREE SURVIVAL (bDFS): is measured as time to PSA failure. While earlier reports of prostate cancer patients treated with radiotherapy have used the ASTRO consensus definition (ACD) of PSA failure, recent studies^{71,72,73} have suggested the "nadir+2" definition is a more sensitive and specific definition of biochemical failure. Indeed, a recent expert panel met in Phoenix⁷⁴ and developed a consensus recommendation using the later definition. So that comparisons can be made with earlier literature, both definitions shall be used:
 - 9.4.1.1 Phoenix definition: failure occurs when the PSA is ≥ 2 ng/ml more than the lowest PSA measurement before the current one, with no backdating. Administration of salvage therapy (hormones, surgery, etc...) will be considered failure.
 - 9.4.1.2 Strict ASTRO Consensus Definition (ACD): failure is defined as three consecutive rises in post-treatment PSA, measured at the specified follow-up intervals. If three consecutive PSA rises occur during the first 2 years after treatment, followed by a non-hormonal induced PSA decline, this will not be considered a failure. Administration of salvage therapy (hormones, surgery, etc...) will be considered failure. Failure date is the midpoint between the dates of the last non-rising PSA and the first PSA rise.
 - 9.4.2 CRITERIA FOR LOCAL FAILURE: clinical evidence of local progression or recurrence. Clinical failure includes a palpable abnormality that has increased in size, failure of regression of a palpable abnormality by 2 years after treatment, or redevelopment of a prostate abnormality after complete response. Patients with a prostate abnormality compatible with local recurrence, or a PSA failure shall undergo a prostate biopsy. Histologic criteria for local failure is a positive prostate biopsy more than 2 years after treatment. Patients with a normal exam and no evidence of PSA failure shall be considered controlled locally. Patients with clinical failure and no biopsy are considered local failures. If a patient is locally

controlled at the time of orchiectomy or androgen ablation, he is censored and considered "not evaluable" for further local control.

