9.4.3 CRITERIA FOR NONLOCAL FAILURE

- 9.4.3.1 DISTANT FAILURE (includes regional failure): documented if clinical, bone scan, CT or other imaging study shows metastatic disease. Biochemical failure with a negative prostate biopsy shall be considered distant only failure. Biopsy of metastatic site required if radiographic or clinical findings are equivocal. Type of metastatic failure (distant and/or regional) shall be recorded if known. Prostate biopsy recommended at this time.
- 9.4.3.2 DISEASE-FREE SURVIVAL: for any measure of disease, including PE, PSA, bone scan, CT/MRI and biopsy, or death.
- 9.4.3.3 DISEASE-SPECIFIC SURVIVAL: for any of the following:
 - 9.4.3.3.1 Death due to prostate cancer.
 - 9.4.3.3.2 Death due to other causes, with active malignancy (defined by clinical or biochemical evidence of progression). If a patient suffered a previous relapse, but has inactive disease, this is not considered a disease-specific death.
 - 9.4.3.3.3 Death due to complications of treatment.
- 9.4.3.4 OVERALL SURVIVAL: for death from any cause

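### Sections 9.4.2 and 9.4.3.1 do not define local and distant failure uniquely: two kinds of patient receive conflicting labels and a third receives none

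*Combined protocol and SAP*

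**What the plan says.** Section 9.4.2 opens by basing local failure on clinical evidence of progression or recurrence. It then adds rules in sequence:

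- Biopsy trigger: "Patients with a prostate abnormality compatible with local recurrence, or a PSA failure shall undergo a prostate biopsy". No time limit is attached, so this includes the first two years.
- Histology: "Histologic criteria for local failure is a positive prostate biopsy more than 2 years after treatment". No condition is placed on exam or PSA.
- Control: "Patients with a normal exam and no evidence of PSA failure shall be considered controlled locally". No condition is placed on the biopsy result.
- Clinical failure without histology: "Patients with clinical failure and no biopsy are considered local failures".
- A man who is locally controlled when androgen ablation starts is censored for local control.

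Section 9.4.3.1 gives two routes to distant failure. It is "documented if clinical, bone scan, CT or other imaging study shows metastatic disease", and in addition: "Biochemical failure with a negative prostate biopsy shall be considered distant only failure".

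Section 9.1.5 requires a biopsy at biochemical or local clinical failure. Biopsy otherwise "is encouraged at 2 years following treatment and at time of distant failure". Section 9.4.1 defines PSA failure in two ways, Phoenix and ASTRO, and 9.4.2 does not say which one it means. Local and distant failure are secondary objectives in Section 2.0 and are analysed by Kaplan-Meier under Section 11.4.2.3.

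**The concern.** A Kaplan-Meier analysis needs every man to have exactly one status at each time: event, at risk, or censored. The sentences above were written as separate rules with no order of precedence, and nothing ensures that they are exclusive or exhaustive. If two rules apply to the same man, his status depends on which sentence the coder reads. If no rule applies, the coder must invent one.

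The most consequential case is a biopsy-proven recurrence that one sentence codes as local failure and the next codes as local control. Local status also determines who is censored at androgen ablation, so an unclear label makes the censoring unclear too.

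**Working it through.** The documents state no local or distant failure rate and no sample size for these endpoints, so there is no figure to reproduce. The check is to apply the rules literally to every combination of findings.

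**Inputs**
- Exam: normal, or clinical failure (9.4.2).
- PSA failure: no or yes (9.4.1).
- Biopsy: none, negative, positive at 2 years or earlier, positive beyond 2 years (9.1.5, 9.4.2).
- Metastasis shown: no or yes (9.4.3.1).

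This gives 2 × 2 × 4 × 2 = 32 states.

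**Rules as coded**
- Local failure: clinical failure on exam, or positive biopsy beyond 2 years.
- Locally controlled: normal exam and no PSA failure.
- Distant failure: metastasis shown, or PSA failure with a negative biopsy (the latter labelled distant only).

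**States that are contradictory or empty**

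| Case | Exam | PSA failure | Biopsy | Metastasis shown | Label under the rules |
|---|---|---|---|---|---|
| 1 | Normal | No | Positive, beyond 2 years | No or yes (2 states) | Local failure and locally controlled |
| 2 | Clinical failure | Yes | Negative | No or yes (2 states) | Local failure and distant only |
| 3a | Normal | Yes | Positive, at 2 years or earlier | No | None |
| 3b | Normal | Yes | None | No | None |

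Case 3 needs all its conditions. If the exam shows clinical failure the man is local, and if metastasis is shown he is distant. Case 3b arises only when the biopsy required at PSA failure was not done.

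**Size.** The enrolment targets in 11.2.5 are 190 low-risk and 129 intermediate-risk men, 319 in total. One relabelled man moves a crude rate by:
- 1/190 = 0.53 percentage points (low risk)
- 1/129 = 0.78 points (intermediate risk)
- 1/319 = 0.31 points (all)

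The number of such men cannot be derived, because the documents give neither uptake of the encouraged biopsy nor its positivity. Purely as assumptions:
- Case 1: if 10% to 50% of men have the encouraged biopsy beyond the 2-year point, and 5% to 20% of those are positive with normal exam and PSA, it covers 0.10 × 0.05 = 0.5% to 0.50 × 0.20 = 10% of men (about 1 to 19 of 190).
- Case 3a: if 1% to 3% have PSA failure within 2 years and 20% to 50% of those have a positive biopsy, it covers 0.01 × 0.20 = 0.2% to 0.03 × 0.50 = 1.5% (0.4 to 2.9 of 190).

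Ranges this wide show that the effect could be negligible or visible. They are not estimates.

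**The case against.** The best defence is that a sensible coder would manage. The control sentence can be read as a default for men who were not biopsied, with the histologic rule governing those who were. The sentence on clinical failure without a biopsy may similarly hint that histology decides when it is available, which would take the man in case 2 out of local failure. A man in case 3 can be treated as having no local or distant event yet. He is not lost to the trial: he counts in bDFS, and disease-free survival in 9.4.3.2 takes any measure of disease, including PSA and biopsy. Coding conventions may also exist in the case report forms, which Appendix IV only references.

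These readings are reasonable, but the text states none of them. The control sentence is mandatory and has no biopsy exception, and the opening criterion of 9.4.2 rests on clinical evidence alone. Treating case 3 as event-free leaves open what happens if he then starts androgen ablation, because the censoring rule applies only to men who are locally controlled. The defence does establish that case 3 is a gap and not a contradiction, and that case 1 arises mainly through an optional biopsy.

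A reader might infer three stronger points that the documents do not support:

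- *That the 2-year cut is itself contradictory because it sits at the 24-month visit.* A man with normal exam, no PSA failure and a positive biopsy at 2 years or earlier has one clear label, locally controlled. The ±2-week window in 9.1.4 belongs to a list of assessments that does not name biopsy. Any cut-point divides cases near it.
- *That calling PSA failure with a negative biopsy distant only is an error.* It is an explicit convention added to the imaging rule. The sentence asking for biopsy of a metastatic site concerns equivocal findings, not negative scans. The convention has a cost in interpretation, but it is a choice.
- *That the number of men wrongly called distant can be read off the expected PSA failures.* That needs the share of negative biopsies, which is not given, and it would size the convention and not the defects above.

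**Conclusion.** The point holds as a defect of definition: four states carry two incompatible labels and two carry none. A reader might go on to say that the local and distant failure rates are wrong. That is not shown. The rates are not uniquely defined, and the ambiguity affects results only if such men occur.

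The consequence is limited to secondary, descriptive Kaplan-Meier endpoints without hypothesis tests. With few failures expected, the per-man shift of about half a percentage point in the low-risk cohort could still be noticeable. The conclusion rests on a literal reading of 9.4.2 and 9.4.3.1 and assumes that no coding rule outside the documents settles the cases. It is worth correcting because the correction is nearly free, not because it threatens the trial's main conclusions.

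**What to change.** Amend 9.4.2 and 9.4.3.1, or add a coding rule to Section 11.4.2.3, so that every man has one local and one distant status:

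1. Make local control conditional on a normal exam, no PSA failure and no qualifying positive biopsy. A positive biopsy beyond 2 years then overrides a normal exam and PSA.
2. State which label governs clinical failure plus PSA failure with a negative biopsy.
3. Assign a category to PSA failure with a normal exam and no metastasis shown: for example, local failure if the early biopsy is positive, and biochemical failure of unknown site if no biopsy was done. State the event or censoring status that follows in each analysis, including when androgen ablation begins.
4. State whether Phoenix or ASTRO defines PSA failure in these rules.
5. Keep the distant-only convention for PSA failure with a negative biopsy, but report those men separately from men with metastasis shown.

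This changes endpoint coding only. It uses biopsy, exam, PSA and imaging results that the protocol already requires or encourages. The cost is minor recoding of collected data, and the local failure rate may rise slightly.

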9.4.3 CRITERIA FOR NONLOCAL FAILURE

- 9.4.3.1 DISTANT FAILURE (includes regional failure): documented if clinical, bone scan, CT or other imaging study shows metastatic disease. Biochemical failure with a negative prostate biopsy shall be considered distant only failure. Biopsy of metastatic site required if radiographic or clinical findings are equivocal. Type of metastatic failure (distant and/or regional) shall be recorded if known. Prostate biopsy recommended at this time.
- 9.4.3.2 DISEASE-FREE SURVIVAL: for any measure of disease, including PE, PSA, bone scan, CT/MRI and biopsy, or death.
- 9.4.3.3 DISEASE-SPECIFIC SURVIVAL: for any of the following:
 - 9.4.3.3.1 Death due to prostate cancer.
 - 9.4.3.3.2 Death due to other causes, with active malignancy (defined by clinical or biochemical evidence of progression). If a patient suffered a previous relapse, but has inactive disease, this is not considered a disease-specific death.
 - 9.4.3.3.3 Death due to complications of treatment.
- 9.4.3.4 OVERALL SURVIVAL: for death from any cause

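### Distant failure combines shown spread with PSA failure after a negative prostate biopsy, and the plan does not report the two apart

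*Combined protocol and SAP*

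**What the plan says.** Section 9.4.3.1 places distant failure, which includes regional failure, under the heading of nonlocal failure and gives two routes to it.

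- **Documented.** It is "documented if clinical, bone scan, CT or other imaging study shows metastatic disease". For doubtful cases the section adds "Biopsy of metastatic site required if radiographic or clinical findings are equivocal".
- **Inferred.** "Biochemical failure with a negative prostate biopsy shall be considered distant only failure". No imaging condition is attached.

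Two tests are due at PSA failure. Section 9.1.5 states "PROSTATE BIOPSY will be performed at time of biochemical or local clinical failure", and Section 9.1.6 states "BONE SCAN will be performed at the time of biochemical failure".

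Section 9.4.1 keeps two definitions of biochemical failure. Under Phoenix (9.4.1.1), "failure occurs when the PSA is ≥ 2 ng/ml more than the lowest PSA measurement before the current one, with no backdating". Under ASTRO (9.4.1.2), "failure is defined as three consecutive rises in post-treatment PSA, measured at the specified follow-up intervals", with the failure date set back to a midpoint. Section 9.4.3.1 does not say which definition triggers the inferred route.

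Distant failure is a secondary objective (Section 2.0). Section 11.4.2.3 applies Kaplan-Meier analysis to the outcomes as Section 9.4 defines them, including distant control, and does not separate the two routes.

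**The concern.** A distant-control curve is normally read as freedom from regional or metastatic disease. Here some of its events may rest only on a PSA rise and a prostate biopsy that found no cancer. The bone scan that could help to tell these men apart is required, yet the inferred route does not use it. The section treats evidence unevenly: an equivocal finding calls for tissue from the metastatic site, whereas a clearly negative scan with a negative prostate biopsy still gives a distant failure.

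At stake is the meaning of one reported figure. A reader of the results could not tell how many of the distant failures had shown disease, and could not compare the rate with a series that counted shown disease only.

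**Working it through.** No sample size, power, error rate or stopping rule rests on distant failure, so there is no plan figure to reproduce. The check is a reading of the sections together, followed by a calculation of scale.

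**Step 1: apply the rules to the possible cases.**

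| Case | Result under the text |
|---|---|
| Metastatic disease shown clinically or on imaging | Distant failure, documented |
| PSA failure, prostate biopsy negative, scan equivocal | Site biopsy required, but already a distant failure by the inferred route whatever it shows |
| PSA failure, prostate biopsy negative, bone scan negative | Distant failure, inferred |
| Phoenix rise of 2 ng/ml or more that later falls, prostate biopsy negative | Distant failure, inferred: 9.4.1.1 has no exception for a later fall |
| Three rises in the first 2 years, then a non-hormonal fall, Phoenix not met | Not a failure under 9.4.1.2, so the inferred route is not triggered |

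The third and fourth rows are the point. No section exempts these men, gives them a category of their own, or asks for an analysis without them.

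**Step 2: date the inferred event.** Section 9.4 measures intervals from enrolment, but 9.4.3.1 gives no date for an inferred failure. Three dates are open: the Phoenix date (not backdated), the ASTRO midpoint (backdated) and the date of the negative biopsy. The curve depends on the choice.

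**Step 3: scale, low-risk cohort.**

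Inputs: assumed 5-year bDFS 97.5%, performance criterion 93%, and 150 evaluable men (Section 11.2.2); 190 low-risk men enrolled (Section 11.2.5).

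PSA failures = n × (1 − bDFS):

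- 150 × 0.025 = 3.75 and 150 × 0.07 = 10.5
- 190 × 0.025 = 4.75 and 190 × 0.07 = 13.3

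Let s be the share of PSA failures with a negative prostate biopsy. The documents give no value, so s runs from 0 to 1 as an assumption. Percentage points added to distant failure = s × (1 − bDFS) × 100:

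| s (assumed) | bDFS 97.5% | bDFS 93% |
|---|---|---|
| 0 | 0 | 0 |
| 0.5 | 1.25 | 3.5 |
| 1 | 2.5 | 7.0 |

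These are crude 5-year proportions. They are upper values for each s, because a man in this group whose metastasis is shown would count by the documented route anyway. The plan gives no expected bDFS for the intermediate-risk cohort, so it is left out.

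**The case against.** The strongest reply is that the second sentence is a deliberate attribution rule. The heading is nonlocal failure, regional failure is included, and the type is recorded only if known, so the plan expects nonlocal failures of unknown site. If the prostate biopsy is negative, the PSA must be attributed somewhere. The endpoint is secondary and descriptive, and the rule can only add distant failures, which counts against the device. Dropping it would leave biopsy-negative PSA failures without a place in the local/nonlocal split.

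All of that stands, and it rules out some stronger readings:

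- A reader might infer that the two sentences contradict each other. They are two routes to one category, so this is a mixed definition.
- A reader might infer that men without metastasis are being counted. A negative bone scan does not show that: the endpoint includes regional disease, and the bone scan is the only imaging that Section 9.1.6 requires at biochemical failure. The supportable statement is that no spread has been shown.
- A reader might infer that an early ASTRO bounce leaves a man wrongly labelled as a distant failure. Section 9.4.1.2 covers the case of "If three consecutive PSA rises occur during the first 2 years after treatment, followed by a non-hormonal induced PSA decline" and says it is not a failure, so the inferred route has no trigger. Only the Phoenix definition lacks such an exception.

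The reply does not show that the combined figure can be read as shown disease. That the rule was intended does not tell the reader how many events came by each route.

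**Conclusion.** The point holds as a reporting weakness in a secondary endpoint. Followed as written, the plan yields a distant-failure rate and curve that mix shown disease with inferred disease. The primary bDFS and toxicity endpoints, the sample size, the futility analysis and the safety stopping rule are untouched.

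The size is 0 to 2.5 percentage points at the plan's assumed low-risk bDFS and 0 to 7 at the 93% criterion. Both ranges rest on an assumed biopsy-negative share of 0% to 100%.

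A reader might go further and say that the curve would consist largely of PSA-only events, or that the rate would be many times the documented one. The documents do not support either. Both need a metastasis rate and a biopsy-negative share that the plan does not give, and the ratio also depends on how far men with metastases and men with PSA failure overlap. The gap between ASTRO and Phoenix results in Table 1 concerns biochemical control. It is a reason to name the definition, but it says nothing about distant failure or biopsy results.

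**What to change.** In Sections 9.4.3.1 and 11.4.2.3, classify each distant failure by its basis:

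- (a) documented regional or metastatic disease, on clinical, imaging or biopsy evidence;
- (b) inferred from biochemical failure with a negative prostate biopsy, no metastasis having been found.

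Report the distant-control Kaplan-Meier estimate for (a) alone, and for (a) and (b) combined. For (b), state which PSA definition triggers it and which date is the event date. The label for (b) should say that no metastasis was found, not that there was none.

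The cost is wording, one more table row and one more curve. PSA, prostate biopsy and bone scan at biochemical failure are already required. The documented-only figure will differ from series that used the combined definition; the combined line covers that comparison.
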